Evidence-based care of NAFLD in T2D: Intervention content will include: 1) NAFLD education; 2) diet/lifestyle support; 3) T2D medication management; and 4) clinically-indicated liver testing and care. [name] (PI) and the Clinical Research Coordinator (CRC) will deliver NAFLD education and diet/lifestyle support content. [name] (PI) will conduct medication management, which will involve review of glycemic trends, assessment of hypoglycemia and adjustment of the T2D regimen to accommodate initiation of pioglitazone, GLP-1RA and/or SGLT2i. The order in which these medications are considered will depend on clinical judgement, patient preference and cost, but GLP-1RA will be prioritized as appropriate, since this class has potent weight loss effects.¹⁶ Also, at baseline (and as indicated throughout the study), [name] (PI) will review clinical data and order clinically-indicated liver testing based on guidelines. Surveys and clinical evaluation will be repeated at study conclusion. A treatment acceptability measure (TAP)²⁰ will be administered at conclusion to gauge intervention acceptability. A detailed summary of data collection and outcome measures can be seen in Table 3.

Table 3: Detailed summary of data collection and outcomes	Method	Timing
Primary outcomes		
Feasibility		
System-level NAFLD detection	Patients who met criteria for NAFLD after chart review / total number of potentially-eligible patients based on our EHR criteria	3 months
Recruitment rate*	Patients eligible and sent letter or MyChart message / Patients enrolled	3 months
Retention rate	Patients enrolled / Patients completed study	3 months
Visit completion rate	Total study visits completed / total study visits scheduled	3 months
Acceptability		
	TAP measure ²⁰	3 months
	Qualitative interviews	3 months
Secondary outcomes of interest		
Medication changes made during the study	Study visit notes in EHR	0, 3 months
Proportion of patients in whom clinically-indicated tests were ordered (e.g. labs, referral, imaging).	Study visit notes in HER	0, 3 months
Psychosocial constructs Self-efficacy Autonomy support Quality of life	6-item SEMCD ²¹ HCCQ Diabetes ¹⁸ SF-12 ¹⁹	0,3 months
Descriptive data to characterize population		
Social and demographic Age, sex, race/ethnicity, marital status, education, employment, tobacco use, alcohol use, SDOH screen (food insecurity, housing instability, lack of transportation)	Self-reported surveys	0 months
Health literacy/numeracy	NVS	0 months

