Medication adherence	VMNQ ²²	0 months
Clinical Baseline knowledge of NAFLD, years with diabetes, medical history, medication use	Self-reported surveys	0 months

Improving detection and evidence-based care of NAFLD in Latinx and Black patients with type 2 diabetes (NAFLD-DM): A pilot study

PI: [name]

Page 5 of 7

Version 2: May 31, 2024

Labs: HbA1c, AST, ALT	Use from EHR if collected within 3 months of baseline visit. Otherwise, research labs collected in DUHS at specified time points.	0 months
Biomedical Height, weight, BMI	From EHR (last recorded values)	0 months

*We will also track the number of participants who expressed interest in the study based on our recruitment flyer, and examine the recruitment rate via this approach (i.e., patients who expressed interest / patients enrolled. **Abbreviations:** TAP=Treatment Acceptability & Preferences; SDOH=social determinates of health; NAFLD=nonalcoholic fatty liver disease; BMI=body mass index; HER=electronic health record; SEMCD=Self-efficacy to Manage Chronic Disease Scale; VMNQ=Voils Medication Non-Adherence Questionnaire; NVS=Newest Vital Sign; HCCQ=Healthcare Climate Questionnaire.

Participant interviews: At study conclusion, individual 30-minute virtual interviews will be conducted with all study participants. The primary purpose will be to assess intervention acceptability and to gain specific feedback about intervention content. Thematic saturation is expected by 12 interviews.²²

Quantitative analysis: Intervention feasibility will be evaluated by examining recruitment rates, retention rates, and study visit completion rates. For the TAP measure, mean score and standard deviation will be calculated. This feasibility pilot will not be powered to examine changes in clinical measures (e.g., HbA1c, ALT).

Qualitative analysis: All interviews will be digitally recorded and transcribed. Transcripts will be analyzed with direct content analysis.²³

Improving detection and evidence-based care of NAFLD in Latinx and Black patients with type 2 diabetes (NAFLD-DM): A pilot study

PI: [name]

Page 6 of 7

Version 2: May 31, 2024

References

2. Diabetes Mellitus. *Federal Practitioner*. 2017;

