Official Title: Improving Detection and Evidence-based Care of NAFLD in Latinx and Black Patients With Type 2 Diabetes (NAFLD-DM): A Pilot Study

NCT: NCT05844137

IRB Document Date: 5/31/2024

Statistical Design and Power

V: May 31,2024

We expect to enroll 15 participants who self-identify as Black or African American (AA), and 15 participants who self-identify as Hispanic/Latinx.

Our quantitative primary outcomes will be feasibility and acceptability, as below:

| | |
|---|--|
| Feasibility of system-level NAFLD detection approach | Patients who met criteria for NAFLD after chart review / total number of potentially-eligible patients based on our EHR criteria. We will deem this approach feasible if detection rates are >70%. |
| Feasibility of patient-level management | We will assess recruitment rates, retention rates and study visit completion rates. We will consider our management approach to be feasible if we can recruit at least 10 Black/AA patients and 10 Hispanic/Latinx patients over 12 weeks (3 months) |
| Acceptability of intervention by participants | We will calculate the mean and standard deviation of the Treatment Acceptability and Preferences (TAP) measure at 3 months; a score >3 will be deemed acceptable. |

Secondary outcomes: Patient-level outcomes will be examined at 12 weeks (3 months), and these include: hemoglobin A1c, alanine aminotransferase level (ALT), and survey measures (i.e., self-efficacy, perceived autonomy support and quality of life). Effect size of the pre-post difference and 95% confidence intervals will be calculated.

This pilot study will not have enough statistical power to establish effectiveness of the intervention for these secondary outcomes. Results of an intervention to improve NAFLD detection and management in Black and/or Hispanic/Latinx persons with T2D has not been previously reported. Therefore, the primary goal of this pilot study is to generate evidence in this area to estimate effect sizes and show feasibility of the intervention to guide future work.

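### Protocol Table 3 defines the recruitment and retention rates, both primary feasibility outcomes, upside down, so the values rise as performance worsens

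*Protocol*

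**What the plan says.** Protocol Table 3, under primary outcomes (feasibility), gives a ratio for each of four measures, and its footnote adds a fifth:

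- System-level detection: "Patients who met criteria for NAFLD after chart review / total number of potentially-eligible patients based on our EHR criteria"
- Recruitment rate: "Patients eligible and sent letter or MyChart message / Patients enrolled"
- Retention rate: "Patients enrolled / Patients completed study"
- Visit completion rate: "Total study visits completed / total study visits scheduled"
- Footnote, flyer route: the team will "examine the recruitment rate via this approach (i.e., patients who expressed interest / patients enrolled"

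The protocol's quantitative analysis paragraph says "Intervention feasibility will be evaluated by examining recruitment rates, retention rates, and study visit completion rates" and gives no formula. The SAP, in its row on feasibility of patient-level management, says "We will assess recruitment rates, retention rates and study visit completion rates", also without a formula. The SAP's criterion in that row is a count: the approach is feasible if the team can "recruit at least 10 Black/AA patients and 10 Hispanic/Latinx patients over 12 weeks".

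**The concern.** A recruitment rate is normally the share of those approached who enrol, and a retention rate the share of those enrolled who finish. Table 3 has both the other way up, and so does the footnote. Table 3 is the only place in either document where these two outcomes are given an operational definition, so an analyst who follows the plan would compute reciprocals.

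At stake is the reporting of two primary outcomes in a pilot whose stated purpose includes showing feasibility to guide later work. A reader planning the next study would find recruitment and retention figures that exceed 100%, that increase with poorer uptake or more dropout, and that move opposite to the visit-completion figure in the adjacent row. The alternative is that the team computes the usual rates and so departs, without saying so, from its own definition of a primary outcome.

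**Working it through.** The documents state no numerical recruitment or retention rate, so there is no published figure to reproduce. The check evaluates each ratio as written and reversed.

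**Inputs**

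- Invited: 50, the initial batch to be contacted (Protocol, detection of NAFLD in T2D). The protocol expects more than 2,000 eligible patients and does not say whether more than 50 would be invited, so 100 is added as an assumed alternative.
- Enrolled: 20 (SAP floor, 10 + 10) or 30 (SAP expectation, 15 + 15). The protocol's range of 10 to 15 per group gives the same limits.
- Completers: not given in the documents. I assume 27, 24 and 15 of 30.
- All enrollees are assumed to come from letters or MyChart messages.

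**Which way the slash runs.** The detection and visit-completion rows both read achieved / possible. The SAP repeats the detection ratio and applies a threshold of more than 70% to it, which makes sense only as numerator over denominator. The footnote introduces its ratio with i.e., as the meaning of the recruitment rate. The slash therefore reads as division.

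**Recruitment:** as written = invited / enrolled; reversed = enrolled / invited. Values are shown as percentages for comparison.

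| Invited | Enrolled | As written | Reversed |
|---|---|---|---|
| 50 | 20 | 50/20 = 250% | 20/50 = 40% |
| 50 | 30 | 50/30 = 167% | 30/50 = 60% |
| 100 (assumed) | 20 | 100/20 = 500% | 20/100 = 20% |
| 100 (assumed) | 30 | 100/30 = 333% | 30/100 = 30% |

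For either number invited, the better enrolment gets the lower value as written.

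**Retention, 30 enrolled:** as written = enrolled / completed; reversed = completed / enrolled.

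| Completed (assumed) | As written | Reversed |
|---|---|---|
| 30 | 30/30 = 100% | 30/30 = 100% |
| 27 | 30/27 = 111% | 27/30 = 90% |
| 24 | 30/24 = 125% | 24/30 = 80% |
| 15 | 30/15 = 200% | 15/30 = 50% |

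The direction does not depend on the assumed counts. Completers cannot outnumber enrollees, so enrolled / completed is at least 1, equals 1 only if everyone completes, and grows with each dropout. At equal performance of 80%, the visit-completion row would read 80% and the retention row 125%.

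**The case against.** The best case on the other side is that this is loose notation with little consequence. The three reversed expressions follow the order of patient flow (contacted or interested, then enrolled, then completed), under a column headed Method, and could be shorthand for going from one count to the next. The names of the outcomes make the intent plain, and a retention value above 100% would expose the slip at once. No test, interval, sample size or feasibility threshold uses either ratio, and the underlying counts are collected the same way whichever is on top. The documents do not express these two rates as percentages, and the completer counts and the figure of 100 invited are assumptions.

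Much of this stands, and it limits the importance of the point. The SAP's count-based rule is not affected, and no data are lost. The two rows that run the other way do not prove how the team would compute the other three. But shorthand for patient flow does not explain why ratios in the same column run in both directions, nor why the footnote presents its ratio as what the recruitment rate means. That the slip would probably be noticed is a reason to correct it now, since the only written definition of two primary outcomes would otherwise have to be ignored. The assumed counts affect the illustrated sizes, not the direction.

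**Conclusion.** The concern holds. As written, the recruitment rate, the retention rate and the flyer recruitment rate are reciprocals of the intended quantities, and they increase as performance falls. At the documents' own figures of 50 invited and 20 to 30 enrolled, recruitment would read 250% to 167% instead of 40% to 60%, assuming that exactly 50 are invited and that all enrollees come from that route. Retention would read 125% instead of 80% if 24 of 30 completed, and could not read below 100% under any outcome.

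This is an error of outcome definition and reporting. It does not change the SAP's decision on patient-level feasibility, and the intended values can be recovered by taking the reciprocal. It should be fixed because these are primary outcomes and the correction is trivial.

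**What to change.** In Protocol Table 3 and its footnote, reverse the three ratios:

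- Recruitment rate = patients enrolled / eligible patients sent a letter or MyChart message.
- Flyer recruitment rate = patients enrolled via the flyer / patients who expressed interest via the flyer.
- Retention rate = patients who completed the study / patients enrolled.

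A minor clarification belongs with the first: count only letter or MyChart enrollees in its numerator, because the flyer route runs in parallel and its enrollees are not in that denominator.

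The cost is a wording change in two table rows and one footnote. It needs no extra patients or visits, and no change to the SAP or its count-based rule.

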Official Title: Improving Detection and Evidence-based Care of NAFLD in Latinx and Black Patients With Type 2 Diabetes (NAFLD-DM): A Pilot Study

NCT: NCT05844137

IRB Document Date: 5/31/2024

Statistical Design and Power

V: May 31,2024

We expect to enroll 15 participants who self-identify as Black or African American (AA), and 15 participants who self-identify as Hispanic/Latinx.

Our quantitative primary outcomes will be feasibility and acceptability, as below:

| | |
|---|--|
| Feasibility of system-level NAFLD detection approach | Patients who met criteria for NAFLD after chart review / total number of potentially-eligible patients based on our EHR criteria. We will deem this approach feasible if detection rates are >70%. |
| Feasibility of patient-level management | We will assess recruitment rates, retention rates and study visit completion rates. We will consider our management approach to be feasible if we can recruit at least 10 Black/AA patients and 10 Hispanic/Latinx patients over 12 weeks (3 months) |
| Acceptability of intervention by participants | We will calculate the mean and standard deviation of the Treatment Acceptability and Preferences (TAP) measure at 3 months; a score >3 will be deemed acceptable. |

Secondary outcomes: Patient-level outcomes will be examined at 12 weeks (3 months), and these include: hemoglobin A1c, alanine aminotransferase level (ALT), and survey measures (i.e., self-efficacy, perceived autonomy support and quality of life). Effect size of the pre-post difference and 95% confidence intervals will be calculated.

This pilot study will not have enough statistical power to establish effectiveness of the intervention for these secondary outcomes. Results of an intervention to improve NAFLD detection and management in Black and/or Hispanic/Latinx persons with T2D has not been previously reported. Therefore, the primary goal of this pilot study is to generate evidence in this area to estimate effect sizes and show feasibility of the intervention to guide future work.

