Once identified, patients will receive the following guideline-concordant content as part of the intervention: a) diet/lifestyle support, with counseling on hypocaloric diet and moderate-intensity exercise;⁵ b) NAFLD education;⁵ c) medication management, with proactive use of T2D medications known to be protective against NAFLD progression (pioglitazone, GLP-1RA, SGLT2i);^{5, 7, 16} and d) clinically-indicated liver testing and care based on guidelines.⁵ The content of this intervention will be delivered remotely via telehealth approaches. In order to ensure feasibility within the proposed KL2 timeline, we have limited the pilot duration to 3 months. This will allow time to observe change in liver enzymes, as well as HbA1c. Table 1

shows when intervention content will be delivered throughout the

Study population: We will enroll 10-15 Latinx/Hispanic and 10-15 Black patients with T2D and NAFLD, based on elevated ALT and exclusion of other liver diseases (e.g., viral hepatitis, alcohol abuse).

Research activity:

Detection of NAFLD in T2D: The Duke DEDUCE tool will be used to generate a report of potentially eligible Latinx and Black patients with an ICD code for T2D (E11.xx) and at least one ALT >40 IU/mL in males or > 31 IU/mL in females¹⁷ in the preceding 12 months. For this feasibility pilot, we will also restrict eligibility to patients who have a PCP or Endocrinologist in DUHS to facilitate communication regarding T2D medication changes during the study period. We anticipate >2,000 patient will meet our inclusion and exclusion criteria. A report will be exported from DEDUCE and I will review the charts of potentially eligible patients to exclude individuals with liver dysfunction likely due to an etiology other than NAFLD. We will not exclude patients with an ICD-10 code for NASH (K75.81), as long as they are not medically optimized (i.e. on pioglitazone and GLP-1RA), since these individuals serve to benefit from the intervention.

The first 50 patients who meet eligibility will be mailed a letter or sent a MyChart message with opt-out instructions. Patients who do not opt out will be contacted by phone and, if interested, they will sign an e-

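### The SAP's pass rule for patient-level management tests recruitment only, and Protocol Table 3 and its footnote print the retention and recruitment ratios upside down

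*SAP*

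**What the plan says.** In the SAP's table of primary outcomes, the row on feasibility of patient-level management opens with three measures: "We will assess recruitment rates, retention rates and study visit completion rates". The next sentence gives the only criterion: "We will consider our management approach to be feasible if we can recruit at least 10 Black/AA patients and 10 Hispanic/Latinx patients", over 12 weeks. No threshold is attached to retention or visit completion. The other two rows set their thresholds on the quantity they name: detection above 70%, and a TAP score above 3.

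The protocol's Study population paragraph sets the enrolment range: "We will enroll 10-15 Latinx/Hispanic and 10-15 Black patients with T2D and NAFLD". The SAP expects 15 in each group. The protocol's Quantitative analysis paragraph says "Intervention feasibility will be evaluated by examining recruitment rates, retention rates, and study visit completion rates", again without thresholds.

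Protocol Table 3 lists the feasibility rates among the primary outcomes. Retention is "Patients enrolled / Patients completed study" and recruitment is "Patients eligible and sent letter or MyChart message / Patients enrolled". The table's footnote gives the flyer route as "patients who expressed interest / patients enrolled". In the same table, system-level detection and visit completion have the achieved count on top and the total below.

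**The concern.** The management content is delivered after enrolment. Table 1 places diet and lifestyle sessions at months 0, 1 and 2, and medication changes and tests as needed up to month 3. A count of people who signed up cannot show whether that content can be delivered. The SAP's stated conclusion on management could therefore sit beside retention and visit-completion figures that contradict it. This matters because the SAP gives showing feasibility, as a guide to later work, as part of the pilot's primary goal.

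The inverted ratios are a separate problem. If they are computed as defined, worse retention gives a larger retention rate and better recruitment gives a smaller recruitment rate.

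**Working it through.** **The criterion against the planned enrolment.** There is no power or sample-size calculation to reproduce; both 10 + 10 and 15 + 15 are stated without derivation.

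- Protocol minimum: 10 per group, 10 + 10 = 20. The SAP criterion is the same number.
- SAP expectation: 15 + 15 = 30. The criterion is 20/30 = two-thirds of it.

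So reaching the planned minimum on time is by itself enough to pass.

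**Holding recruitment fixed and varying completers.** The documents give no expected retention, so the completer counts below are assumptions for illustration. Enrolment is taken as 10 + 10 or 15 + 15, reached within 12 weeks. Intervals are exact (Clopper-Pearson) 95%.

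| Enrolled | Completed | SAP label | Completed / enrolled (95% CI) | Retention as printed (enrolled / completed) |
|---|---|---|---|---|
| 20 | 0 | feasible | 0% (0 to 17%) | undefined |
| 20 | 10 | feasible | 50% (27 to 73%) | 20/10 = 200% |
| 20 | 16 | feasible | 80% (56 to 94%) | 20/16 = 125% |
| 20 | 20 | feasible | 100% (83 to 100%) | 20/20 = 100% |
| 30 | 15 | feasible | 50% (31 to 69%) | 30/15 = 200% |
| 30 | 20 | feasible | 67% (47 to 83%) | 30/20 = 150% |

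The third column never changes, because neither retention nor visit completion enters the rule. That follows from the wording and does not depend on the counts chosen.

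**The printed ratios.**

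- Retention: completers cannot exceed enrolled, so enrolled / completed is at least 1. It rises with dropout and has no value when nobody completes.
- Recruitment: the protocol states "The first 50 patients who meet eligibility will be mailed a letter or sent a MyChart message with opt-out instructions". Assume that 50 is the full number sent and that nobody enrols through the flyer. If 20 enrol, the printed ratio is 50/20 = 250%, against 20/50 = 40% (95% CI 26 to 55%) the right way up. If 30 enrol, it is 50/30 = 167%, against 30/50 = 60%. The printed figure falls as recruitment improves.
- Flyer route: interested / enrolled is likewise at least 1, provided that every flyer enrollee first expressed interest.

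**Link between the two defects.** The SAP criterion is a count of enrolled patients and uses none of these ratios. Correcting them leaves its verdict unchanged.

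**The case against.** The strongest defence is that the 10 + 10 rule is one numerical benchmark within a broader descriptive evaluation. The sentence just before it in the SAP names all three measures, and the protocol says that feasibility will be judged by examining all three. This stands in part. A reader might infer that retention and visit completion are ignored or will go unreported, and the documents do not support that. What they do show is that the one stated criterion for calling management feasible leaves both out.

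It can also be said that 10 + 10 is not trivial, since it demands both groups and has a deadline. That is fair, but it makes the rule a reasonable test of recruitment, not of management.

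On the ratios, the defence is that these are evident slips and that a retention rate of 150% would be noticed. Probably so. They nonetheless occur three times in the current definitions of primary-outcome rates, and two neighbouring ratios in the same table are the right way up, so inversion is not a convention of the table.

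A reader might go further and want visit completion recast to exclude month 0, because early contacts can mask later dropout. The documents do not support calling that ratio wrong: completed over scheduled is correctly oriented. Table 1 also places the only NAFLD education session, and one of the three diet and lifestyle sessions, at month 0, so excluding it would remove part of the intervention from the measure.

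**Conclusion.** The point holds in two limited respects.

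First, the SAP's label for patient-level management is decided by recruitment alone, at the protocol's own enrolment floor. Retention anywhere from 0% to 100% leaves it unchanged. This rests only on the wording of the SAP row. The harm is a stated conclusion that can mislead; data are not hidden, and the documents attach no stop/go decision to the label.

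Second, three rates in Table 3 and its footnote are inverted. The size depends on the data: 150% instead of 67% if 20 of 30 complete, and 250% instead of 40% if 20 of 50 invited patients enrol. A reader might infer that this inversion corrupts the SAP's feasibility verdict. It does not, because that verdict uses a count; the error is confined to the reported rates.

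**What to change.** **SAP, row on patient-level management.** Rename the 10 + 10 criterion *recruitment feasibility*. Base the statement about management on retention and visit completion, each with a 95% confidence interval. Use an exact interval for retention. For visit completion, use one that allows for repeated visits within a participant: Table 1 has 8 required contacts per person (1 enrolment, 2 surveys, 1 education, 3 diet and lifestyle, 1 interview), so 8 × 20 = 160 to 8 × 30 = 240 contacts come from only 20 to 30 people. If enrolment has begun, date the change and disclose it.

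**Protocol Table 3 and footnote.** Print:

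- retention as completed / enrolled;
- recruitment as enrolled through letter or MyChart / eligible and sent either one. The denominator should not be shortened to *contacted*, because the protocol uses that word for the later phone call to those who did not opt out;
- flyer recruitment as enrolled through the flyer / expressed interest through the flyer.

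Leave the visit-completion ratio as it is.

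**Cost.** This is rewording, with no new data collection. The drawback is that management then has no single pass/fail answer. A joint rule that adds a minimum retention is optional, for the sponsor to choose and justify, and it would be imprecise at this size. As an illustration only, take an 80% cut-off, meaning at least 16 of 20 or 24 of 30. With true retention of 80% it is met with binomial probability 0.63 or 0.61, so it fails 37% or 39% of the time. With true retention of 60% it is met with probability 0.05 or 0.02. A cut-off added after enrolment has begun may also look post hoc.
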